16.0 STATISTICAL CONSIDERATIONS

16.1 Statistical Overview

The purpose of this study is to evaluate continued safety and efficacy of the AtriCure Synergy Ablation System during commercial use in real world settings for surgical ablation of non-paroxysmal atrial fibrillation during concomitant cardiac surgical procedures.

16.2 Analysis Populations

The primary analysis population will consist of patients who received the AtriCure Synergy Ablation System for treatment of non-paroxysmal atrial fibrillation in the setting of a concomitant cardiac surgical procedure. Other sub-populations will be detailed in the statistical analysis plan.

The primary study outcomes will also be stratified according to primary cardiac surgical procedure type, e.g.:

- (1) CABG
- (2) Aortic Valve
- (3) Mitral Valve
- (4) Tricuspid Valve, and

(5) Multiple procedures

We will stratify enrolled subjects by type of primary cardiac surgical procedure to assure a reasonable precision of the estimate for serious device or procedure related SAEs within each specified stratum.

In addition, primary study outcomes will be stratified by "new users" versus "existing users". A "new user" is defined as a site that has not performed the Maze IV procedure in the past, or has not performed the procedure with the AtriCure Synergy Ablation System. An "existing user" is defined as a site that performs the MAZE IV procedure using the AtriCure Synergy Ablation System.

16.3 Sample Size Calculations and Assumptions

The study will enroll up to 390 subjects at 50 North American centers. This number of subjects shall provide an adequate sample to fully assess the outcome of the procedure within a broad population.

The patient sample size for this study was derived to establish that the rates for the primary outcomes of 30-day serious device and ablation procedure related AE and 3-year efficacy success rates are within the pre-established reference rate bounds. This number of subjects shall provide an adequate sample to fully assess the outcome of the procedure within a broad population and should supply a sufficient number of subjects for both 30 day safety evaluation (>333 subjects at 30 days) and long term efficacy evaluation (>275 subjects at 3 years). Should the statistical power be sufficient with fewer than 390 subjects (at least 333 subjects at 30 days), PAS will stop recruitment early and continue to follow those subjects currently enrolled.

16.4 Safety

The primary safety objective of the ABLATE Post Approval Study (ABLATE PAS) is to demonstrate that the serious device and ablation procedure related AE rate (excluding pacemaker implantation) within 30 days or prior to discharge (whichever is later) of the AtriCure Synergy Ablation System is no worse than a performance goal derived from the non-paroxysmal AF subject cohort of the combined AtriCure IDE ABLATE and ABLATE AF clinical trials.

The rate of serious device or ablation procedure related adverse events (excluding pacemaker implantation) within 30 days or prior to discharge (whichever is later) in the non-paroxysmal AF subject cohort of the combined AtriCure IDE ABLATE and ABLATE AF clinical trials was 6.25% (4/64).

The acceptable upper limit of the serious device and ablation procedure related AE rate for the ABLATE PAS trial (i.e. the performance goal) is established at 10%.

The primary safety hypotheses for this study are stated as follows:

 $H_0: \pi_{PAS_SAFETY} \ge 10\%$ $H_1: \pi_{PAS_SAFETY} < 10\%$

Using a one-sided exact binomial test for proportions at the 0.05 overall level of significance, a total of 333 subjects are required to demonstrate that the 30 day serious device or procedure related AErate

(excluding pacemaker implantation) in subjects treated with the AtriCure Synergy Ablation System is < 10% (the performance goal) with 80% power. This calculation was completed using PASS 2008 Power and Sample Size Software by NCSS.

A maximum of 15% Loss to Follow-Up (LTFU) is anticipated through 30 days, as such the sample size for enrollment is increased to 390 subjects to ensure a minimum of 333 subjects are available for assessment of the primary safety endpoint through 30 days. Should LTFU be less than 15%, enrollment will stop early given the safety endpoint is powered to at least 80%.

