16.6 Statistical Analyses

Primary Analysis

Serious device and ablation procedure related AE rates and confidence intervals will be summarized at discharge, 30 days, and 1-year with a hypothesis test performed on the cumulative 30 day serious device

and ablation procedure related AE rate. The primary safety hypothesis test will be conducted using a one-sided exact binomial test for proportions at the 0.05 overall level of significance.

The efficacy outcome rate of freedom from AF, off antiarrhythmic drugs along with confidence intervals will be summarized at 1, 2 and 3 years (i.e. 12. 24, 36 month follow-up), with a hypothesis test performed on the 3-year success outcome. The primary efficacy hypothesis test will be conducted using a one-sided exact binomial test for proportions at the 0.05 overall level of significance.

Secondary Analysis

Secondary outcomes will be summarized for the analysis population and certain sub-populations. Two-sided 95% confidence intervals will be calculated for all presented rates. Descriptive analyses will be provided for patient demographics, clinical device/procedural success, medical histories, and comorbidities. Logistic regression analyses may be used to screen a wide range of parameters for their association with some outcomes.

Procedures to Account for Missing Data

Reasonable efforts will be made to obtain complete data for all patients; however, missing observations will occur due to patients lost to follow-up or noncompliance with required assessments. The reasons for missing data will be evaluated (e.g. patient is deceased, lost to follow up, missed visit, etc.). In addition, the distribution of prognostic factors between patients with data and those without data will be examined to evaluate any potential sources of bias.

Any missing observations will be described in detail and evaluated for assessment of possible bias. For the primary analysis of safety and efficacy outcomes, missing data will be imputed using multiple imputation methods (e.g. SAS PROC MI). Additional sensitivity analyses of missing data including 1) considering everyone who was a failure at last visit also a failure at 3 years and multiple imputation on everyone who was a success at last visit, 2) including everyone LTFU as a failure and 3) a tipping point analysis will also be performed.

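### With 390 enrolled, the plan's own 15% maximum loss leaves 331.5 evaluable rather than 333, and having at least 333 does not by itself secure 80% exact power for the primary safety test

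*Combined protocol and SAP*

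**What the plan says.** Section 16.4 sizes the trial on safety: a performance goal of 10%, a historical rate of 6.25% (4/64), and 333 subjects for 80% power, "Using a one-sided exact binomial test for proportions at the 0.05 overall level of significance". Section 16.6 repeats the same test for the analysis: "one-sided exact binomial test for proportions at the 0.05 overall level of significance". Section 16.4 then anticipates at most 15% loss through 30 days and states that "the sample size for enrollment is increased to 390 subjects to ensure a minimum of 333 subjects are available". Section 16.3 caps enrolment at 390.

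Two sentences govern an early end to recruitment. Section 16.3: "Should the statistical power be sufficient with fewer than 390 subjects (at least 333 subjects at 30 days), PAS will stop recruitment early". Section 16.4: "Should LTFU be less than 15%, enrollment will stop early given the safety endpoint is powered to at least 80" per cent. Section 16.3 also describes the 30-day count a second way: "30 day safety evaluation (>333 subjects at 30 days".

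On missing outcomes, Section 16.6 says: "For the primary analysis of safety and efficacy outcomes, missing data will be imputed using multiple imputation methods".

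**The concern.** There are two linked problems.

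First, the inflation for loss does not deliver what it promises. At the stated maximum loss, the enrolment cap yields fewer than 333 subjects, and the plan has no reserve above 390.

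Second, 333 is treated as a floor above which power is adequate. The power of an exact binomial test does not rise steadily with sample size. It jumps when one more event is allowed and then drifts down until the next jump. 333 sits on such a jump, so sizes just below it and many sizes above it have lower power.

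Section 16.5 says that the safety endpoint drives the sample size, so this is the study's governing power claim. The study is a condition of device approval, and the regulator would be relying on an 80% figure that holds only at certain sizes.

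**Working it through.** **Inputs.** From Section 16.4: null rate 10%, one-sided exact binomial test at 0.05, target power 80%, 333 evaluable, maximum loss 15%, 390 enrolled. Assumption: a true rate of 6.25%. Section 16.4 gives this as the historical rate but does not name it as the design alternative.

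**Method.** For each evaluable size n, let c be the largest integer with P(X ≤ c | n, 0.10) ≤ 0.05. The goal is met if events ≤ c. Power is P(X ≤ c | n, 0.0625).

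**Step 1: reproduce 333.** At n = 333, c = 24, the exact one-sided level is 0.0492 and power is 80.1%. No smaller n reaches 80%. The plan's figure therefore reproduces, and this supports 6.25% as the alternative used. Nearby rates give a different smallest n: 321 at 6.2% and 345 at 6.3%.

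**Step 2: inflation for loss.**
- 390 × 0.85 = 331.5, which is below 333.
- 333 / 0.85 = 391.8, which rounds up to 392.
- (390 − 333) / 390 = 57/390 = 14.6%, the largest loss that 390 can absorb.
- If each subject independently has a 15% chance of loss, 390 enrolled gives fewer than 333 evaluable with probability 55%.

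**Step 3: power around and above 333 (true rate 6.25%).**

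| Evaluable n | Events allowed (c) | Exact level | Power |
|---|---|---|---|
| 331 | 23 | 0.0344 | 74.5% |
| 332 | 23 | 0.0331 | 74.0% |
| 333 | 24 | 0.0492 | 80.1% |
| 334 | 24 | 0.0475 | 79.7% |
| 344 | 24 | 0.0328 | 75.4% |
| 355 | 25 | 0.0337 | 77.1% |
| 367 | 26 | 0.0334 | 78.3% |
| 378 | 27 | 0.0342 | 79.8% |
| 379 | 28 | 0.0493 | 84.6% |
| 390 | 28 | 0.0337 | 80.8% |

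Power is below 80% at 334–344 (11 sizes), 348–355 (8), 363–367 (5) and 378 (1). That is 25 of the 58 sizes from 333 to 390. Sixteen of these fall short by less than 2 points; the other nine (339–344 and 353–355) fall short by more. From 379 upward power is at least 80% at every size (checked to 699). Reaching 379 from 390 enrolled needs a loss of at most 11/390 = 2.8%.

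**Step 4: average over chance variation in loss.** With 390 enrolled and the evaluable number distributed as Binomial(390, 1 − loss), mean power is 77.0% at 15% loss, 79.3% at 10% and 81.4% at 5%. It reaches 80% at a loss of about 8.5% or less.

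**Step 5: sensitivity to the inferred alternative, sizes 333–390.** At 6.0%, power runs from 81.2% to 89.1%, with no shortfall. At 6.5%, it runs from 68.9% to 79.3%, and all 58 sizes are below 80%.

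**The case against.** The best case for the plan has four parts.

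*The inflation slip is rounding.* 390 against 392 is two subjects, and enrolling 392 would hardly help: at 15% loss its mean power is 77.2%, against 77.0% for 390. This stands as a comment on size. The claim that 333 is guaranteed is still wrong at the plan's own maximum loss.

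*The saw-tooth belongs to every exact design.* The plan says only that 333 gives 80%, which is true. Mean power over 333–390 is 80.4%, most of the shortfalls are small, and the type I error is controlled at every size. All of this stands, so the validity of the test is not in question. It does not rescue the use of 333 as a power floor in the stopping text.

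*The stopping text already requires sufficient power.* Section 16.3 makes power the condition, and Section 16.4 can be read as making 80% a requirement. On that reading a stop at 344 would not be allowed. The reading is fair, but the Section 16.4 sentence can equally be taken to say that 80% follows from the lower loss. Neither section says how power is to be checked, and the only number offered is 333. The alternative wording in Section 16.3 starts at 334, which gives 79.7%.

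*The percentages are conditional.* They rest on an unstated alternative drawn from 4 events in 64 subjects, and on a test of observed subjects, whereas Section 16.6 imputes missing safety outcomes. Both limits stand. Power under imputation was not calculated here. The sizing text is nevertheless written in terms of subjects available for assessment, and imputation does not recover the information lost.

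**Conclusion.** The concern holds. Whatever event rate is assumed, 390 enrolled does not secure 333 evaluable at a 15% loss; it covers 14.6%. On the inferred 6.25% alternative and a test on observed subjects, the two-subject gap costs about 6 points of power (80.1% at 333, 74.5% at 331). A stop guided by the 333 count can then end as low as 75.4%. A 0.25-point change in the assumed rate either removes the shortfall over 333–390 or extends it to every size in that range, so the alternative needs to be on the page. This should be corrected: it affects the accuracy of the stated power and the stopping rule, not the validity of the test.

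**What to change.** In Sections 16.3 and 16.4:

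- State the 6.25% alternative.
- State that 390 covers a loss of up to 14.6%, and drop the claim that it guarantees 333 at 15%.
- Restate safety power as about 74–80% for 331–344 evaluable subjects, and as at least 80% at every size only from 379.
- Use one wording for the 30-day count: either more than 333 or at least 333.
- In the early-stop rule, replace the 333 count with a requirement that exact power be at least 80% over the range of evaluable sizes projected at the time of stopping. If this is not met, enrol to 390 and report the exact power at the size obtained. Enrolling to 390 does not in itself restore 80% when losses are high.
- Say whether the power statement refers to observed subjects or to the imputed primary analysis in Section 16.6.

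The cost is restated figures in two sections and one sentence in the stopping rule, with no increase in the cap of 390. In practice the stricter condition will often be hard to meet below 379, so early stopping would be used less. That follows from applying the plan's own 80% condition.

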16.5 Efficacy

Based on data collected from the non-paroxysmal AF subject cohort of the AtriCure IDE ABLATE clinical trial it is estimated that approximately 55-60% of patients treated with the AtriCure Synergy Ablation System will be free of AF while off AADs at 2-3 years follow-up, where free of AF is defined as no episode of atrial fibrillation, atrial flutter or atrial tachycardia lasting longer than 30 seconds. This estimate is based on the 57.8% success rate (26/45) seen at an average follow-up time of 20 months in the subset of non-paroxysmal AF subjects treated under the AtriCure IDE ABLATE trial.

he primary efficacy hypotheses for this study are stated as follows:	
escuming a success rate of E7.99/ and a loss to follow up that only leaves 250 of the initial 200 nations	
Assuming a success rate of 57.8% and a loss to follow-up that only leaves 250 of the initial 390 patient	.S
valuable at 3 years, this test of efficacy superiority with a significance level of 0.05 can	i
. Since this is even greater than , the ABLATE PAS sample size is driven by the	
afety primary endpoint.	

16.6 Statistical Analyses

Primary Analysis

Serious device and ablation procedure related AE rates and confidence intervals will be summarized at discharge, 30 days, and 1-year with a hypothesis test performed on the cumulative 30 day serious device

and ablation procedure related AE rate. The primary safety hypothesis test will be conducted using a one-sided exact binomial test for proportions at the 0.05 overall level of significance.

The efficacy outcome rate of freedom from AF, off antiarrhythmic drugs along with confidence intervals will be summarized at 1, 2 and 3 years (i.e. 12. 24, 36 month follow-up), with a hypothesis test performed on the 3-year success outcome. The primary efficacy hypothesis test will be conducted using a one-sided exact binomial test for proportions at the 0.05 overall level of significance.

Secondary Analysis

Secondary outcomes will be summarized for the analysis population and certain sub-populations. Two-sided 95% confidence intervals will be calculated for all presented rates. Descriptive analyses will be provided for patient demographics, clinical device/procedural success, medical histories, and comorbidities. Logistic regression analyses may be used to screen a wide range of parameters for their association with some outcomes.

Procedures to Account for Missing Data

Reasonable efforts will be made to obtain complete data for all patients; however, missing observations will occur due to patients lost to follow-up or noncompliance with required assessments. The reasons for missing data will be evaluated (e.g. patient is deceased, lost to follow up, missed visit, etc.). In addition, the distribution of prognostic factors between patients with data and those without data will be examined to evaluate any potential sources of bias.

Any missing observations will be described in detail and evaluated for assessment of possible bias. For the primary analysis of safety and efficacy outcomes, missing data will be imputed using multiple imputation methods (e.g. SAS PROC MI). Additional sensitivity analyses of missing data including 1) considering everyone who was a failure at last visit also a failure at 3 years and multiple imputation on everyone who was a success at last visit, 2) including everyone LTFU as a failure and 3) a tipping point analysis will also be performed.

17.0 QUALITY CONTROL AND QUALITY ASSURANCE

17.1 Protocol Deviations

A protocol deviation is a failure to comply with the requirements specified within this clinical study protocol. Examples of protocol deviations may include enrollment of a study patient who does not meet all of the inclusion/exclusion criteria specified in the protocol and missed study visits without documentation. Each investigator shall conduct this clinical study in accordance with this clinical study protocol, regulatory body regulations, ISO guidelines, Good Clinical Practices, and any conditions of approval imposed by their IRB.

All deviations are reviewed and assessed for their impact on patient safety by AtriCure or designee. The site PI and study staff is responsible for knowing and adhering to their IRB/EC reporting requirements.

The protocol deviations for this protocol consist of, but not limited to the following:

- Failure to obtain patient's informed consent prior to any study-related activities and the index procedure
- Use of other approved devices for the ablation procedure or MAZE IV procedure, or lesion set deviations.
- Failure to conduct protocol required clinical follow-ups
- Failure to conduct protocol required clinical follow-ups within time windows
- Failure to report serious adverse events according to protocol requirements.

In the event of any deviation from the protocol, the Investigator will be notified of the site's non-compliance. Corrective actions will be required, if necessary. Continued protocol deviations despite reeducation of the study site personnel or persistent protocol deviation may result in termination of the site's study participation. Patients already enrolled at these sites will continue to be follow per the clinical protocol.

17.2 Investigator / Investigational Site Training

AtriCure and/or designated CRO will be responsible for providing training to the investigator and appropriate clinical site personnel.

17.3 Monitor Training

AtriCure and/or designated monitors will be trained appropriately to monitor study progress including but not limited to the protocol and CRFs.

17.4 Study Monitoring

A study specific monitoring plan will be conducted to ensure protocol compliance and applicable regulatory requirements.

Clinical monitors will verify patient data and ensure compliance with GCP, clinical protocol and other study requirements, according to the guidelines set forth in the monitoring Standard Operating Procedures (SOP) and ISO 14155 guidelines to be utilized for the study.

17.5 Site Monitoring

AtriCure or designee may conduct periodic compliance assessments at various study sites. AtriCure or designee may request access to all trial records including source documentation for inspection and photocopying during a compliance assessment. The Investigator and research coordinator must be available to respond to reasonable requests and queries made during the compliance assessment process.

17.6 Regulatory Agency Inspection

In the event that an investigator is contacted by a regulatory agency regarding this trial, the investigator will notify AtriCure or its designee immediately. The investigator and research coordinator must be available to respond to reasonable requests and queries made during the inspection process. The

AtriCure Inc.

Page 32 of 46

CONFIDENTIAL

Rev. M

investigator must provide AtriCure or designee with copies of all correspondence that may affect review of the current trial (e.g., Form FDA 483, Inspectional Observations and Warning Letters). AtriCure may provide needed assistance in responding to regulatory audits.

18.0 ETHICS/PROTECTION OF HUMAN SUBJECTS

18.1 Ethical Standard

The investigator will ensure that this study is conducted in full conformity with the principles set forth in The Belmont Report: Ethical Principles and Guidelines for the Protection of Human Subjects of Research, as drafted by the US National Commission for the Protection of Human Subjects of Biomedical and Behavioral Research (April 18, 1979) and codified in 45 CFR Part 46 and/or the ICH E6; 62 Federal Regulations 25691 (1997), the Declaration of Helsinki, CIOMS, and the International Ethical Guidelines for Biomedical Research Involving Human Subjects (2002).

18.2 Institutional Review Board/Ethics Committee

Each participating institution must provide for the review and approval of this protocol and the associated informed consent documents and recruitment material by an appropriate Ethics Committee(EC)/Institutional Review Board (IRB). Any amendments to the protocol or consent materials must also be approved before they are placed into use.

18.3 Informed Consent Process

Informed consent is a process that is initiated prior to the individual's agreeing to participate in the study and continues throughout the individual's study participation. Extensive discussion of risks and possible benefits of this therapy will be provided to the subjects and their families. Consent forms describing in detail the study interventions/products, study procedures, and risks are given to the subject and written documentation of informed consent is required prior to starting intervention/administering study product. Consent forms will be IRB-approved and the subject will be asked to read and review the document. Upon reviewing the document, the investigator will explain the research study to the subject and answer any questions that may arise. The subject will sign the informed consent document prior to any procedures being done specifically for the study. The subjects should have the opportunity to discuss the study with their surrogates or think about it prior to agreeing to participate. The subjects may withdraw consent at any time throughout the course of the trial. A copy of the informed consent document will be given to the subjects for their records. The rights and welfare of the subjects will be protected by emphasizing to them that the quality of their medical care will not be adversely affected if they decline to participate in this study.

